2.1 Study Design

This was a researcher-initiated, multicenter, randomized controlled trial conducted in six first-class general hospitals in China's Zhejiang, Fujian, Jiangsu, and Liaoning provinces. Twelve IV nurse specialists were involved in performing the catheterizations. The research protocol was based on assigning patients to three different catheter tip placement groups and observing the relationship between tip placement and catheter-related complications. The institutional review board approved the research protocol of each participating hospital according to the Helsinki Declaration that respects individuals and recognizes vulnerable groups. All the participants had the right to make informed decisions. (IRB:20200107-11). Patients who underwent MC placement in all six hospitals were enrolled, and the study was conducted between September 2020 and January 2021.

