2.3 Sampling

A general formula-based sample estimation method using the data on the relationship between MC tip position and catheter-related complications was used to calculate the sample size (Wu et al., 2020). Based on the selected reference, the incidence of complications at the tip of the MC at the thoracic wall of the axillary vein was 32.5% (Wu et al., 2020), while the incidence of complications in the subclavian vein was 12.5% (Wu et al., 2020). A power analysis was performed to calculate the effect size. Efficacy was set at 0.8 (with an 80% probability of finding a difference between populations) and 0.05 (5% of Type I error). Considering external factors that may have caused loss and withdrawal, each group was increased in size by 20%, to 65 patients per group.

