2.6 Evaluation Indicators and Judgment Criteria

2.6.1 Incidence of Catheter-Related Complications

First, the catheter-related complications were assessed. The complications studied included phlebitis, catheter-related thrombosis, catheter occlusion, catheter dislodgement, bleeding, catheter-related infections, and infiltration. In this assessment, the incidence of each complication (i.e., number of patients with these complications) was divided by the total number of cases. Then, the total number of incidences of catheter-related complications was taken as the main outcome index (i.e., the number of patients with complications/the total number of patients). One patient with one or multiple complications was counted as one case in total.

The judgment criteria for each complication were as follows: ① phlebitis: the relevant contents in the Standard (Gorski et al., 2021) were considered; ② catheter-related thrombosis, also referred to as symptomatic thrombosis, was observed and reported either by patients or bedside nurses. Edema the limbs, neck, shoulder, chest, and/or face on the side of catheterization was observed for and reported to physicians, in order to perform an ultrasound for venous thrombosis detection; ③ catheter-related infections included local infection at the puncture site and catheter-related bloodstream infection, which were evaluated according to the corresponding diagnostic criteria in the Standard (Gorski et al., 2021); ④ catheter occlusion, inability to withdraw blood or sluggish blood return, sluggish flow; resistance or inability to flush lumen, inability to infuse fluid, Frequent occlusion alarms on electronic infusion pump. ⑤ catheter dislodgement included dislodgement of more than 3 cm; ⑥ infiltration was noted when the puncture site had liquid exudation; and ⑦ bleeding referred to the blood exudation at the puncture site 48 h after catheterization.

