**Midline Catheter Tip Positioning and Catheter-Related Complications during
Antimicrobial Therapy: A Multicenter Randomized Controlled Trial**

NCT04601597

April 30, 2021

The current study followed the conformance study protocol analysis and conducted the statistical analysis using SAS 9.4 (<http://www.sas.com/>). The catheter measurement data were represented by mean and standard deviation according to the normal distribution. In contrast, the catheter measurement data with non-normal distribution were represented by median and quartile, and the number of cases or percentages represented the counting data. The catheter-measurement data between the three groups were compared through variance analysis or the Kruskal-Wallis H test. Counting data were compared using the Chi-square test, exact probability method, and Kruskal-Wallis H test. The test level $\alpha=0.05$ for all three groups was a two-sided test, and $P<0.05$ was considered a statistically significant difference. Bonferroni method was used in pairwise comparison to optimize the significance level. The test levels $\alpha=0.017$ and $P<0.017$ were statistically significant differences. To analyze the rate of complications, cumulative event rates were plotted as Kaplan-Meier curve, and differences in these rates were assessed using log-rank tests, and $P<0.0001$ was considered a statistically significant difference. Mann-Whitney U tests were performed to analyze the differences in observed event times.

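### The SAP judges the log-rank test of complications at P<0.0001, against its own levels of 0.05 and 0.017, and gives no reason

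*SAP*

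**What the plan says.** The SAP is one paragraph and sets three significance levels.

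- Three-group comparisons: the 0.05 level "for all three groups was a two-sided test, and $P<0.05$ was considered a statistically significant difference".
- Pairwise comparisons, after Bonferroni: "The test levels $\alpha=0.017$ and $P<0.017$ were statistically significant differences".
- Time to complication, shown as Kaplan-Meier curves of cumulative events. Here the rule for the group comparison is the third level: "differences in these rates were assessed using log-rank tests, and $P<0.0001$ was considered a statistically significant difference".

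For categorical data it says that "Counting data were compared using the Chi-square test, exact probability method, and Kruskal-Wallis H test", without naming the outcomes this covers. Protocol section 2.6.1 defines the main outcome as a proportion, the total complication incidence being "taken as the main outcome index (i.e., the number of patients with complications/the total number of patients". Protocol section 2.3 sizes the trial at a 5% Type I error, with 32.5% complications for a tip in the chest-wall axillary vein, whereas "the incidence of complications in the subclavian vein was 12.5"%. The SAP does not say whether the log-rank test compares three groups or pairs.

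**The concern.** The 0.0001 figure is worded as a decision rule, in the same form as the 0.05 and 0.017 rules before it, and nothing in either document produces it. The main outcome, read as categorical data, keeps 0.05 and 0.017. The same complications analysed as time to event must reach 0.0001. The two analyses can then give opposite verdicts only because their thresholds differ.

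This matters for two reasons. The log-rank test is the only planned comparison of complications that allows for different dwell times and censoring. The log-rank sentence is also the only one in the body of the SAP that mentions complications, so a reader looking there for the rule on the trial's central question finds 0.0001. Complications are a safety outcome, and the rule can present a real difference as non-significant.

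**Working it through.** **Inputs.** Complication rates of 32.5% and 12.5%, power 0.80, Type I error 0.05 and a 20% increase to 65 per group (Protocol 2.3); 110 randomised per group (Protocol 2.4); levels 0.05, 0.017 and 0.0001 (SAP). I also use 88 per group, which is 110 × 0.8, to allow for 20% loss.

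**The plan's own figures.**
- Pairwise level: 0.05/3 = 0.0167, which rounds to the stated 0.017.
- Sample size: n = (z_α + z_β)² × 2p̄(1−p̄)/(p₁−p₂)² with p̄ = 0.225. One-sided 0.05 gives (1.645 + 0.842)² × 0.34875/0.04 = 53.9, and 53.9 × 1.2 = 64.7, so 65. Two-sided 0.05 gives 68.4, and × 1.2 = 82. The stated 65 therefore matches a one-sided level; that is a separate matter, but the design level is 5% either way.

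**Where 0.0001 could come from.** 0.05/0.0001 = 500 and 0.017/0.0001 = 170. A Bonferroni split of 0.05 would need 500 comparisons, while three groups give three pairs. The two-sided critical value rises from 1.96 (at 0.05) or 2.39 (at 0.017) to 3.89.

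**Closed-form power for the pairwise log-rank test.** Assume proportional hazards and equal follow-up. HR = ln(0.875)/ln(0.675) = 0.34, so |ln HR| = 1.08. Events d = n × (0.325 + 0.125). Schoenfeld power = Φ(|ln HR|·√d/2 − z).

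| n per group | d | at 0.05 | at 0.017 | at 0.0001 |
|---|---|---|---|---|
| 65 | 29.25 | 83% | 70% | 17% |
| 88 | 39.6 | 92% | 84% | 31% |
| 110 | 49.5 | 97% | 92% | 46% |

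For 80% power this formula needs 27, 36 and 77 events at the three levels.

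**Simulation with censoring at removal.** Assume exponential event times and removal uniform over days 7 to 21, with hazards set so that the expected proportions with a complication before removal are 32.5% and 12.5%. Both tests were run on the same 8,000 trials at each size.

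| n per group | log-rank at 0.0167 | log-rank at 0.0001 | Chi-square significant at 0.0167, log-rank not at 0.0001 | disagreement, both at 0.0167 |
|---|---|---|---|---|
| 110 | 89% | 38% | 51% | 2% |
| 88 | 81% | 23% | 57% | 4% |

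Repeat runs at 0.0001 gave 35–38% and 22–24%. Removal windows of days 5–14 or 7–30 gave 37–39% and 23–24%. The last column shows that the conflict comes from the threshold and not from a difference between the two tests.

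**Three-group log-rank test.** The documents give no control-group rate, so a range is assumed (110 per group, simulated, removal on days 7–21).

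| assumed control rate | power at 0.0001 |
|---|---|
| 12.5% | 61% |
| 22.5% | 27% |
| 32.5% | 39% |
| 40% | 74% |
| 50% | 98% |

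At 0.05 the same scenarios give 92–100%. With 88 per group, power at 0.0001 runs from 15% to 91%.

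**The case against.** The strongest reply is that little depends on this sentence. The main outcome is a proportion and is most naturally tested by Chi-square at 0.05 and 0.017; a stricter level cannot inflate false positives; and the figure may simply be an observed result. The SAP is written in the past tense and dated April 30, 2021, while "the study was conducted between September 2020 and January 2021". If the log-rank P was indeed below 0.0001, it is significant at every level in the SAP and no power was lost in practice.

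Much of this stands. The error is limited to the log-rank test, and the harm to its verdict is conditional on the P-value lying between 0.0001 and the ordinary level. But the documents do not show which explanation is true. If it is an observed result, the SAP presents a result as a decision rule, which also needs correcting. The SAP also never explicitly assigns the Chi-square test to the main outcome, so the protection is an inference.

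A second reply is that the largest losses are for a pairwise test that the SAP does not specify, and that they rest on assumed event-time and removal patterns. This is fair. The pairwise figure at 110 per group is best read as 35–46% across methods. For a three-group test, power at 0.0001 exceeds 60% at three of the five control rates tried.

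**Conclusion.** The concern holds. The SAP applies an unexplained threshold to one planned analysis of complications, and it contradicts the levels set in the same paragraph. At the planned difference with 110 per group, pairwise log-rank power falls from about 89% at 0.0167 to about 38% at 0.0001 (46% by the closed form). In about half of such trials the Chi-square and log-rank verdicts would conflict because of the threshold alone.

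These sizes assume exponential event times, the stated removal windows and the rates in Protocol 2.3. Power below 50% is shown for the pairwise contrast and for three-group control rates of about 20% to 32.5%, not for every scenario. The inconsistency itself depends on none of these assumptions.

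**What to change.** Remove the 0.0001 threshold. State that the three-group log-rank test uses two-sided 0.05 and that any pairwise log-rank tests use 0.05/3 = 0.0167, matching the other comparisons, and say which of these are planned. If 0.0001 was an observed result, move it to the results.

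Because the SAP postdates the study period, record this as a dated correction with its reason and disclose it in the report. The cost is one sentence and a note; no patients, data or procedures change. If the log-rank P lies between 0.0001 and 0.05 (0.0167 for a pair), its stated verdict changes and the report must say so.

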2.5.3 Catheter Maintenance

As suggested by the relevant literature, members of the research group designed the first draft of the MC tip positioning complication observation table. The observation table was later improved after modification by the IV specialist nurse of each hospital, and a third-party Statistics agent designed the electronic database for research. The collected data included the following two categories: ① baseline data of participants: age, sex, educational background, height, weight, diagnosis, history of thrombosis, surgical trauma, and chronic diseases, hemoglobin concentration, platelet count, white blood cell count, prothrombin time, activated partial thrombin time, history of CVC, PICC, and MC; ② Data on catheterization conditions: number of catheterizations, placement site, placement vein, and successful catheterization with the first attempt; ③ Data on the use and maintenance of catheters: daily catheter function evaluation, assessment of complications, and the time and reason of removal IV lines, and the types of antibiotics used in antimicrobial therapy.

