2.6.2 Indwelling Catheter Duration

Indwelling catheter duration referred to the number of days between the date of catheter placement and removal.

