2.7 Data Collection

Catheterization nurses recorded baseline data prior to catheterization, and only the most recent results were recorded one week prior to catheterization, when multiple laboratory results were available. Catheterization site evaluations were recorded after placement, and patients were followed up for 48 h after catheterization as well as every 7th day by IV specialist nurses to review and record the progress of antimicrobial therapy. The last follow-up was conducted at the time of removal, where the reason for removal was also recorded. In addition, bedside nurses evaluated and recorded catheter functioning and complications daily.

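### The SAP runs Mann-Whitney tests on event times it never defines, and gives the log-rank test a significance threshold that conflicts with its other two

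*SAP*

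**What the plan says.** The SAP's single paragraph covers time to complication in two sentences. The first says that "cumulative event rates were plotted as Kaplan-Meier curve, and differences in these rates were assessed using log-rank tests", with P<0.0001 as the criterion for significance. The second says that "Mann-Whitney U tests were performed to analyze the differences in observed event times". It gives no event, time origin, set of patients, pair of groups or significance level for the Mann-Whitney tests.

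Earlier in the same paragraph, the two-sided level is 0.05 for comparing the three groups. For pairs, "Bonferroni method was used in pairwise comparison to optimize the significance level", which gives 0.017.

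The protocol defines two outcomes. In section 2.6.1, "the total number of incidences of catheter-related complications was taken as the main outcome index", counted as patients with at least one complication over all patients. Section 2.6.2 defines a duration: "Indwelling catheter duration referred to the number of days between the date of catheter placement and removal". No time-to-complication endpoint is defined, although the data for one exist. Section 2.7 says that "bedside nurses evaluated and recorded catheter functioning and complications daily", and section 2.5.3 lists "daily catheter function evaluation, assessment of complications, and the time and reason of removal IV lines" among the data collected.

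**The concern.** A complication time exists only for a patient who had a complication. If those are the times meant, the Mann-Whitney test compares two subsets formed by the outcome after randomisation. Its P value answers how early complications came among those who had them. Printed beside a log-rank result, it could be taken as evidence about risk. If instead every follow-up time were entered, a removal without a complication would be treated as an event.

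The natural remedy is to rely on the planned log-rank test, but its threshold disagrees with the rest of the paragraph. Under P<0.0001, a difference of the size used for planning could be declared non-significant by a test that would declare it significant at the SAP's own pairwise level.

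**Working it through.** **Inputs from the documents.** Planning complication rates are 32.5% (axillary vein, chest wall) and 12.5% (subclavian vein), from protocol section 2.3. No control-group rate is given. There are 110 patients per group (section 2.4). The loss allowance is 20% (section 2.3); applied to 110 it gives 110 × 0.8 = 88, which I use as a lower case. The documents give no timing of complications, so all timing below is assumed.

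**The plan's own level.** Bonferroni for three pairs: 0.05 / 3 = 0.0167, which reproduces 0.017. By contrast 0.05 / 0.0001 = 500, so P<0.0001 does not follow from any number of comparisons in this trial.

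**Patients in an events-only Mann-Whitney test.**
- n = 110: 110 × 0.325 = 35.75 and 110 × 0.125 = 13.75, so about 50 of 220 enter.
- n = 88: 88 × 0.325 = 28.6 and 88 × 0.125 = 11.0, so about 40 of 176 enter.
- Share left out: 1 − (0.325 + 0.125)/2 = 77.5%.

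**Why it says little about risk.** Take exponential times over an assumed fixed 14 days. The median time among patients with an event is 14 × ln(1 − p/2) / ln(1 − p).
- p = 0.325: 14 × 0.1773 / 0.3930 = 6.3 days.
- p = 0.125: 14 × 0.0645 / 0.1335 = 6.8 days.

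The risks differ by 20 percentage points, but the event times differ by half a day.

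**Simulation of both tests.** Exponential complication times were calibrated to 32.5% and 12.5%, with removal uniform on days 7-14, 7-21, 7-28 or 1-30, times in whole days, and 2,000 trials per cell.

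| Test, 32.5% vs 12.5% | Level | n = 110 | n = 88 |
|---|---|---|---|
| Mann-Whitney, events only | 0.05 | 4.6-6.8% (both sizes) | |
| Mann-Whitney, events only | 0.017 | 1.5-2.4% (both sizes) | |
| Pairwise log-rank | 0.017 | 89.6-92.5% | 80.5-83.7% |
| Pairwise log-rank | 0.0001 | 36.4-43.2% | 21.1-28.1% |

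Repeat runs agreed closely. The Mann-Whitney rate at 0.05 stayed between about 5% and 8%, and log-rank power at 0.0001 fell to 33% at the lowest for n = 110.

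**Hand check of the log-rank figures.** Hazard ratio = ln(0.675)/ln(0.875) = 0.3930/0.1335 = 2.94, with log 1.080. Expected z = 1.080 × √D / 2, where D is the number of events.
- n = 110, D = 49.5: z = 3.80. Power at 0.017 is Φ(3.80 − 2.39) = 92%; at 0.0001 it is Φ(3.80 − 3.89) = 46%.
- n = 88, D = 39.6: z = 3.40. Power is Φ(3.40 − 2.39) = 84% and Φ(3.40 − 3.89) = 31%.

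This large-sample formula runs slightly above the simulation at 0.0001 and shows the same drop.

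**Three-group log-rank at 0.0001.** With the control rate assumed anywhere from 12.5% to 50% and removal uniform on days 7-14 or 7-28 (1,000 trials per cell), power runs from about 28% to 99% at n = 110 and from 16% to 93% at n = 88. At n = 110 it exceeds 50% for assumed control rates of 12.5%, 40% and 50%.

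**The case against.** The best defence is that the event times are indwelling durations. Duration is the only time variable the protocol defines, and Mann-Whitney is a usual pairwise follow-up to the Kruskal-Wallis test the SAP plans. Section 2.2 excludes patients planning discharge with the catheter, and section 2.7 places the last follow-up at removal, so duration is observed for everyone who does not withdraw. This stands: on that reading no selection arises and only wording is missing. The order of the SAP's sentences favours complication times but does not settle the matter. A reader might infer that the SAP certainly tests an outcome-selected subset; the documents do not establish that.

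It can also be said that a near-nominal rejection rate is no malfunction, since the sentence claims to compare times, not risk. That is fair. The harm lies in how the P value may be read beside the log-rank result.

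A reader might go further and infer that the test would make the safer group look worse. With risks fixed at the planning rates, the safer group can be declared earlier at P<0.017 in 79.7% (n = 88) or 89.1% (n = 110) of trials. That requires shared complications on days 1-3 and the excess on days 4-14, windows invented for the purpose. With identical timing the figure is 0.5-0.6%. The documents hold no timing data, so reversal is possible but its likelihood is unknown.

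Finally, a reader might infer that P<0.0001 makes the log-rank test miss the planned difference more often than not. That holds for the pairwise comparison simulated here. It is not general, because the SAP does not say whether the threshold applies to pairs or to three groups, and three-group power depends on a control rate it does not give.

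**Conclusion.** Two defects in the SAP's secondary analysis stand. First, the Mann-Whitney variable is undefined. On the reading its position suggests, the test uses about 50 of 220 patients, chosen by outcome, and rejects at about its nominal rate although the risks differ by 20 points. On the other plausible reading it is acceptable. Second, "differences in these rates were assessed using log-rank tests, and $P<0.0001$ was considered a statistically significant difference" conflicts with the 0.05 and 0.017 set in the same paragraph. For a pairwise test of the planning rates, power is about 80-93% at 0.017 and about 21-43% at 0.0001.

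The power figures assume exponential complication times with proportional hazards, the stated removal windows and 88 to 110 patients per group. The conflict between thresholds needs no assumption.

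A reader might infer that the trial's main conclusion is at risk. It is not on this ground, because the main outcome is a proportion and rests on neither test. The change is worth making, with medium confidence in the adverse reading.

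**What to change.** - **Name the variable.** State the event, time origin, analysis set, pairs and level for the Mann-Whitney tests.
- **If complication times are meant,** drop the Mann-Whitney P value. Show those times descriptively: number of events, median, quartiles. Base inference on the planned Kaplan-Meier and log-rank analysis, with patients in the analysis set who finish follow-up without a complication censored at that point. State whether patients who withdrew under section 2.2 are in that set; the SAP's opening sentence appears to describe a per-protocol analysis.
- **If indwelling duration is meant,** say so, apply 0.017 to each pairwise test, and state how withdrawn patients are handled.
- **Reconcile the log-rank threshold** with the SAP's own levels, 0.05 for three groups and 0.017 for pairs, and report exact P values. Label the change post hoc: the study ran to January 2021 (section 2.1) and the SAP is dated 30 April 2021.

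The cost is a few sentences, with the same data and software, since daily complication records and removal times are already collected. One secondary P value is lost if complication times were meant, and loosening a stated threshold after data collection must be disclosed.
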